6.2. Handling of Partial Dates of Concomitant Medication and Adverse Events

Partial start dates of prior, concomitant medications, and adverse events will be assumed to be the earliest possible date consistent with the partial date. Partial stop dates of prior, concomitant medications, and adverse events will be assumed to be the latest possible date consistent with the partial date. In the case of completely missing stop date, medication will be assumed to be ongoing.

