8.2. Schedule of Visits and Assessments

The schedule of assessments is shown in Table 3.

For a missed visit, the site should attempt to contact the subject to reschedule.

Premature discontinuation procedures are provided in Section 7.3.

Table 3: **Schedule of Assessments**

| | | Treatmo | ent Period ^a | | Follow-up Period ^a |
|---|--|---|------------------------------------|---------------------------|---|
| Visits 1-25 ^b | Transition from Previous Study ^c | Monthly Visits ^d | Quarterly Visits | EOT/ ET | Safety Follow-up Visit ^e |
| | 1 | 2, 3, 5, 6, 8, 9, 11, 12, 14, 15, 17, 18, 20, 21, 23, 24 | 4, 7, 10, 13, 16, 19, 22, 25 | | No later |
| Visits 26-50 ^b | _ | 26, 27, 29, 30, 32, 33, 35, 36, 38, 39, 41, 42, 44, 45, 47, 48 | 28, 31, 34, 37, 40, 43, 46 | No later than Visit 49 | than Visit 50 |
| Qualification/ Safety Assessments | | | | | |
| Informed Consent | X | | | | |
| Eligibility Review | X | | | | |
| Urine Pregnancy Testing (all women) | X | X | X | X | X |
| Urine Drug Screen | X^{f} | | X | | |
| Physical Examination and ECG | | | X | X | |
| Vital Signs | | | X | X | |
| Biochemistry, Hematology, and Urinalysis Samples | | | X | X | |
| Weight and Waist Circumference | | X | X | X | X |
| Adverse Event Monitoring | | X | X | X | X |
| Concomitant Medication Review | | X | X | X | X |
| C-SSRS ^g | | X | X | X | X |
| Psychiatric/ Quality of Life Assessm | nents | | | | |
| CGI-S | | X | X | X | X |
| IWQOL-Lite | | | X | X | |
| Other/ General Procedures | | | | | |
| Study Drug Dispensation | X | X | X | | |
| Study Drug Return Review | | X | X | X | |

Abbreviations: CGI-S=Clinical Global Impressions-Severity; C-SSRS=Columbia-Suicide Severity Scale; ECG=electrocardiogram; EOT=end of treatment; ET=early termination; IWQOL-Lite=Impact of Weight on Quality of Life-Lite

A visit window of ±4 days is allowed throughout the treatment period and the Follow-up period.

- ^b Subjects may be treated with study drug for 24 to 48 months, or until regulatory action; duration will vary by subject.
- ^c Visit 1 must occur within 7 days of the EOT visit of the antecedent studies (ALK3831-A304, ALK3831-A306, or ALK3831-A307) and may occur on the same day. Subsequent visits are to be conducted every month (every 28 days [±4 days]).

 d Except for every 3rd visit from Visit 1 (Quarterly Visits).
- To be performed one month (28 days [±4 days]) after the EOT/ET visit.

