3.2.2. Follow-up Safety Population

Follow-up Safety Population will be defined as subjects in the Safety Population and met any of the following criteria:

- Completed at least one follow-up visit after >7 days of the last dose of ALKS 3831
- Reported at least one AE after >7 days of the last dose of ALKS 3831
- Follow-up Safety Population will be used to analyze the AEs in the safety follow-up period

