3.2.3. Post-discontinuation Safety Population

Post-discontinuation Safety Population will be defined as subjects in the Safety Population and met any of the following criteria:

- Completed at least one follow-up visit >2 days after the last dose of ALKS 3831
- Reported at least one AE >2 days after the last dose of ALKS 3831

AEs to evaluate potential for drug withdrawal and dependence emerging following discontinuation of ALKS 3831 will be assessed for this population, during the period of >2 days to 16 days after the last dose of drug for subjects with at least 4 weeks ALKS 3831 exposure.

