3.8.1. Adverse Events

Incidence of treatment-emergent AEs (TEAEs) will be analyzed as a safety endpoint. Adverse events will be coded by System Organ Class and Preferred Term using the Medical Dictionary for Regulatory Activities (MedDRA[®]) Version 21.0 or higher. The verbatim term will be included in the AE listings.

An AE (coded by preferred term) will be considered a TEAE if the event is newly occurring or worsening on or after the date of first dose of study drug and within 7 days after the last dose of study drug in this study.

An overview table, including number of subjects with TEAEs, AEs leading to treatment discontinuation, study drug related TEAEs, and SAEs will be provided.

The number and percentage of subjects reporting TEAEs during the treatment period will be presented for the following categories:

- System organ class and preferred term
- Preferred term, and including the following subset:
 - TEAEs experienced by $\geq 2\%$ of subjects
- System organ class, preferred term, and severity
- System organ class, preferred term for severe TEAEs
- System organ class, preferred term, and relationship
- System organ class, preferred term for study drug related TEAEs

If the same preferred term occurred more than once for the same subject, the subject will be counted only once for that preferred term using the most severe and most related occurrence for the summarization by severity and by relationship to the study drug.

In addition, the number and percentage of subjects reporting AEs during the safety follow-up period will be tabulated by the system organ class and preferred term.

Subgroup analysis by age (<40 years vs ≥ 40 years), sex (Female vs Male) and race (Black or African American, White, and Other) will be performed for TEAEs during the treatment period by preferred term.

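### The partial-date rule in SAP 6.2 has no first-dose anchor, so some day-missing AEs that began on treatment drop out of the TEAE tables (minor)

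*SAP*

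**What the plan says.** SAP 6.2 covers medications and AEs with a single rule: "Partial start dates of prior, concomitant medications, and adverse events will be assumed to be the earliest possible date consistent with the partial date". It names neither first nor last dose. Partial stop dates go to the latest possible date.

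The onset date then determines the period. Under SAP 3.8.1 an AE is treatment-emergent if it is new or "worsening on or after the date of first dose of study drug and within 7 days after the last dose of study drug". Protocol 14.6 also starts the count at first dose.

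Two further summaries follow last dose:
- Follow-up AEs: "the number and percentage of subjects reporting AEs during the safety follow-up period will be tabulated" (SAP 3.8.1). SAP 3.2.2 places this period more than 7 days after last dose.
- Withdrawal and dependence AEs: assessed "during the period of >2 days to 16 days after the last dose of drug" (SAP 3.2.3).

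The safety follow-up visit is "To be performed one month (28 days [±4 days]) after the EOT/ET visit" (Protocol 8.2, Table 3 notes).

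**The concern.** An imputed onset is never later than the true one, so every error moves an AE earlier. At first dose this works in one direction only. Take first dose on 10 May and a true onset on 20 May recorded as May with no day. The imputed onset is 1 May, and the event is no longer a TEAE. An AE that truly began before first dose is never moved past it.

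The primary objective includes long-term safety, and the rule loses treatment-emergent events in the non-conservative direction, all from the first weeks of treatment.

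The problem is specific to AEs. Concomitant status of a medication depends on use on or after first dose (SAP 3.5), so an early imputed start does not remove it from the summary.

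**Working it through.** The plan gives no figure to reproduce. The check applies the rules to the calendar.

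**Inputs from the documents**
- TEAE window: first dose to last dose + 7 days (SAP 3.8.1).
- Follow-up window: from day 8 after last dose (SAP 3.2.2) to the visit at day 28, range 24 to 32 (Protocol 8.2).
- Withdrawal window: days 3–16 after last dose (SAP 3.2.3).
- One month = 28 days (SAP Table 10), so 24 and 48 months are 672 and 1,344 days.

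**Assumptions**
- Only the day is missing.
- Onset is uniform over time.
- Exposure is at least 28 days.
- The EOT/ET visit falls on the last-dose date.

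**Formula.** Three calendar years including a leap year have 1,096 dates, of which 36 are the 1st of a month, so p = 36/1,096 = 0.03285. A run of i consecutive dates (i ≤ 28) contains no 1st with probability 1 − ip. A day-missing onset is pulled back across a boundary when no 1st lies from the boundary up to the onset. The expected number of onset-days pulled back among the first n after a boundary is S(n) = n − p·n(n+1)/2.

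**First dose**
- Days 1–7: S(7) = 7 − 28p = 6.08; 6.08/7 = 87%.
- Days 1–28: S(28) = 28 − 406p = 14.66; 14.66/28 = 52%.
- Days 29–31 add 0.07, giving 14.73 onset-days per subject.
- Cross-check on one 365-day year: of 5,738 pairs of first-dose date and later onset in the same month, all are misdated except the 365 with first dose on the 1st. 5,373/5,738 = 93.6%, and 5,373/365 = 14.72.

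Share of all day-missing TEAEs lost, 14.73/(exposure + 7):

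| Exposure (days) | Calculation | Lost |
|---|---|---|
| 28 | 14.73/35 | 42% |
| 180 | 14.73/187 | 7.9% |
| 672 | 14.73/679 | 2.2% |
| 1,344 | 14.73/1,351 | 1.1% |

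If 1% to 10% of AEs lacked a day (assumed; the documents give no share), the loss over 48 to 24 months would run from 1% × 1.1% = 0.01% to 10% × 2.2% = 0.22% of all TEAEs.

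**After last dose**
- Follow-up AEs pulled into the TEAE window: S(21) = 21 − 231p = 13.41 of 21, or 64% (70% with the visit at day 24, 57% at day 32).
- Withdrawal AEs moved out: S(14) = 14 − 105p = 10.55 of 14, or 75%. Moved in from days 17–28: 12 × 14p = 5.52. Net (5.52 − 10.55)/14 = −36% (−49% at day 24, −23% at day 32).
- Of the 10.55, those from days 3–7 were already TEAEs: S(5) = 5 − 15p = 4.51.

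**Net TEAE error under the current rule:** (13.41 − 14.73)/679 = −0.2% and /1,351 = −0.1% of day-missing TEAEs. At 180 days it is −1.32/187 = −0.7%.

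**The case against.** The strongest reply is that SAP 6.2 is explicit and programmable, that nothing in either document contradicts it, and that its effect is tiny. The net TEAE change is −0.1% to −0.2% of an unknown and perhaps very small subset. AEs are reviewed monthly, SAP 6.3 asks for missing information to be pursued, and source data are listed. Dataset and programming specifications are separate documents and may hold an anchor. First dose in an extension study is also partly an accounting date. Finally, the remedy replaces a near-zero net error with a larger positive one.

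Most of this stands and limits the severity. It does not remove the error. The small net figure comes from two opposite misplacements: early on-treatment events leave and post-treatment events enter. Queries reduce the number of partial dates but do not classify those that remain. SAP 6.2 refers to no anchor elsewhere. First dose is a real start of samidorphan for any subject who received olanzapine alone in A307, which compares the two (Protocol 5.1).

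A reader might infer more: that AEs vanish, that each AE enters exactly one summary, or that subjects leave the post-treatment populations. The documents do not support this.
- The windows overlap: days 3–7 are in both the TEAE and withdrawal windows, and days 8–16 in both withdrawal and follow-up.
- The AEs displaced after last dose are still counted as TEAEs.
- A subject normally stays in both populations, since either "Completed at least one follow-up visit after >7 days of the last dose of ALKS 3831" or "Completed at least one follow-up visit >2 days after the last dose of ALKS 3831" is sufficient on its own.

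**Conclusion.** The point holds at the first-dose boundary and is minor. Followed as written, SAP 6.2 can only undercount TEAEs there. Under month-only dates and uniform onset, the loss is about 1% to 2% of day-missing TEAEs for subjects treated 48 to 24 months, and more for those who stop early.

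These percentages count events. The tables count each subject once per preferred term, so they are upper bounds for what is reported. Year-only dates fare worse: 96% of onsets in the first 28 days would be dated before treatment.

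The shifts after last dose are secondary. They inflate the TEAE count and thin the follow-up and withdrawal tables. The documents do not support calling any of this a demonstrated bias in the results, because the number of partially dated AEs is not stated and the specifications were not available.

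**What to change.** Add one sentence to SAP 6.2, for AEs only. If the known date parts are compatible with onset on or after first dose and the earliest possible date precedes first dose, impute the first-dose date, unless a recorded stop date (not an imputed one) or the AE record carried over from the antecedent study shows earlier onset. Keep the current rule for medications. If the specifications already hold such an anchor, state it in the SAP.

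**Cost.** A small derivation change, plus linkage to the antecedent-study AE records.

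**Downsides**
- Some day-missing AEs that began just before first dose become TEAEs. The protocol requires that "Visit 1 must occur within 7 days of the EOT visit of the antecedent studies". With onsets reaching back 7 days, equal daily rates and no exception applied, 14.73/(14.73 + 6.08) = 71% of the AEs moved to first dose are true TEAEs. With 28 days it is 14.73/(14.73 + 14.66) = 50%.
- The first-dose loss no longer offsets the post-treatment gain. The net TEAE error becomes 13.41/1,351 = +1.0% to 13.41/679 = +2.0% of day-missing TEAEs (48 to 24 months), and 13.41/187 = +7.2% at 180 days, before any pre-dose onsets are added. This is the conservative direction.

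The fix does not correct the shifts after last dose. A flag in the follow-up and withdrawal outputs, for partially dated AEs that could belong there, is optional disclosure only.

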6.3. Handling of Safety Data

All efforts should be made to obtain the missing information from the investigator. For C-SSRS, vital signs and laboratory testing (chemistry, hematology, urinalysis), only observed data will be used for analyses, and missing data will not be imputed.

7. GENERAL STATISTICAL METHODOLOGY (AND REPORTING OF RESULTS)

In general, summary statistics (n, mean, SD, median, minimum, and maximum for continuous variables, and number and percentage of subjects in each category for categorical variables) will be provided. All summary tables will be based on observed data, and missing values will not be imputed, unless otherwise indicated. Measurements collected from unscheduled visits or repeated assessments will not be included in the by-visit summary tables or figures but will be included in the analyses for the PCS postbaseline values, and subject listings. Source data for the summary tables will be presented as subject data listings.

7.1. Reporting Precision

Summary statistics will be presented to the following degree of precision ([Table 12](#)), unless otherwise specified:

Table 12: Degree of Precision

Statistics	Degree of Precision
Mean, Median, Confidence limit boundaries	One more than the raw data, up to 3 decimal places.
Standard deviation, Standard error	One more than the mean, up to 3 decimal places
Minimum, Maximum	The same as the raw data, up to 2 decimal places
P-value	Rounded to 3 decimal places and therefore presented as 0.xxx; P-values smaller than 0.001 as ‘<0.001’; P-values greater than 0.999 as ‘>0.999’.
Percentage	One decimal place. A percentage of 100% will be reported as 100%. Percentages of zero will be reported as 0.

Fractional numeric values will be presented with a zero to the left of the decimal point (for example, 0.12 – 0.30).

For weight, height, and body mass index (BMI), one decimal place will be used for summary statistics, unless otherwise specified.

8. PROGRAMMING SPECIFICATIONS

Programming specifications will be provided in a separate document.

9. MOCK TABLES, LISTINGS AND FIGURES (TLFS)

Mock-up tables and listings will be provided in a separate document.

10. REFERENCES

APPENDIX 1. AESI - MOVEMENT DISORDERS (INCLUDING EXTRAPYRAMIDAL SYNDROME AND TARDIVE DYSKINESIA; STANDARDIZED MEDDRA QUERY)

Preferred Term (SMQ [#20000095] of Extrapyramidal syndrome)	PT Code
Abnormal involuntary movement scale	10075002
Action tremor	10072413
Akathisia	10001540
Akinesia	10001541
Athetosis	10003620
Ballismus	10058504
Blepharospasm	10005159
Bradykinesia	10006100
Bradyphrenia	10050012
Buccoglossal syndrome	10006532
Chorea	10008748
Choreoathetosis	10008754
Chronic tic disorder	10076661
Cogwheel rigidity	10009848
Complex tic	10076663
Dopamine dysregulation syndrome	10067468
Drooling	10013642
Dyskinesia	10013916
Dyskinesia hyperpyrexia syndrome	10071302
Dyskinesia neonatal	10013922
Dyskinesia oesophageal	10013924
Dysphonia	10013952
Dystonia	10013983
Dystonic tremor	10073210
Emprosthotonus	10014566
Extrapyramidal disorder	10015832
Facial spasm	10063006
Fine motor skill dysfunction	10076288
Freezing phenomenon	10060904

Preferred Term (SMQ [#20000095] of Extrapyramidal syndrome)	PT Code
Gait disturbance	10017577
Gait inability	10017581
Grimacing	10061991
Hyperkinesia	10020651
Hyperkinesia neonatal	10020652
Hypertonia	10020852
Hypertonia neonatal	10048615
Hypokinesia	10021021
Hypokinesia neonatal	10021022
Hypokinetic dysarthria	10082243
Laryngeal tremor	10078751
Laryngospasm	10023891
Meige's syndrome	10027138
Micrographia	10057333
Mobility decreased	10048334
Motor dysfunction	10061296
Movement disorder	10028035
Muscle contractions involuntary	10028293
Muscle rigidity	10028330
Muscle spasms	10028334
Muscle spasticity	10028335
Muscle tightness	10049816
Muscle tone disorder	10072889
Muscle twitching	10028347
Musculoskeletal stiffness	10052904
Oculogyric crisis	10030071
Oesophageal spasm	10030184
On and off phenomenon	10030312
Opisthotonus	10030899
Oromandibular dystonia	10067954
Oropharyngeal spasm	10031111
Parkinsonian crisis	10048868

Preferred Term (SMQ [#20000095] of Extrapyramidal syndrome)	PT Code
Parkinsonian gait	10056242
Parkinsonian rest tremor	10056437
Parkinsonism	10034010
Parkinsonism hyperpyrexia syndrome	10071243
Parkinson's disease	10061536
Parkinson's disease psychosis	10074835
Pharyngeal dyskinesia	10070912
Pharyngeal dystonia	10081226
Pleurothotonus	10035628
Postural reflex impairment	10067206
Postural tremor	10073211
Posture abnormal	10036436
Posturing	10036437
Propulsive gait	10082328
Protrusion tongue	10037076
Provisional tic disorder	10076694
Psychomotor hyperactivity	10037211
Rabbit syndrome	10068395
Reduced facial expression	10078576
Respiratory dyskinesia	10057570
Resting tremor	10071390
Restlessness	10038743
Risus sardonicus	10039198
Secondary tic	10076702
Spasmodic dysphonia	10067672
Status dystonicus	10088053
Tardive dyskinesia	10043118
Tic	10043833
Tongue spasm	10043981
Torticollis	10044074
Torticollis psychogenic	10044076
Tremor	10044565

Preferred Term (SMQ [#20000095] of Extrapyramidal syndrome)	PT Code
Tremor neonatal	10044575
Trismus	10044684
Uvular spasm	10050908
Walking disability	10053204
Writer's cramp	10072249

**APPENDIX 2. AESI - SUICIDAL IDEATION AND BEHAVIOR
(CUSTOM MedDRA QUERY)**

Preferred Term	PT Code
Assisted suicide	10079105
Columbia suicide severity rating scale abnormal	10075616
Completed suicide	10010144
Depression suicidal	10012397
Intentional overdose	10022523
Intentional self-injury	10022524
Overdose	10033295
Poisoning deliberate	10036000
Self-injurious ideation	10051154
Suicidal behaviour	10065604
Suicidal ideation	10042458
Suicide attempt	10042464
Suicide threat	10077417
Suspected suicide	10082458
Suspected suicide attempt	10081704

APPENDIX 3. AE TERMS - ABUSE POTENTIAL (CUSTOM MedDRA QUERY)

Category	Preferred Term	PT Code
Abuse behavior	Accidental overdose	10000381
	Drug abuse	10013654
	Drug abuser	10061111
	Drug detoxification	10052237
	Drug diversion	10066053
	Drug level above therapeutic	10061132
	Drug level increased	10013722
	Drug screen	10050837
	Drug screen positive	10049177
	Drug use disorder	10079381
	Drug use disorder, antepartum	10079382
	Drug use disorder, postpartum	10079383
	Intentional overdose	10022523
	Intentional product misuse	10074903
	Intentional product use issue	10076308
	Maternal use of illicit drugs	10026938
	Needle track marks	10028896
	Neonatal complications of substance abuse	10061862
	Overdose	10033295
	Prescription drug used without a prescription	10076639
	Prescription form tampering	10067669
	Product tampering	10069330
	Reversal of opiate activity	10039004
	Substance abuse	10066169
	Substance abuser	10067688
	Substance use	10070964
	Substance use disorder	10079384
	Substance-induced mood disorder	10072387
	Substance-induced psychotic disorder	10072388
	Toxicity to various agents	10070863

Category	Preferred Term	PT Code
Euphoria related	Euphoric mood	10015535
	Feeling abnormal	10016322
	Feeling drunk	10016330
	Feeling of relaxation	10016352
	Hallucination	10019063
	Hallucination, auditory	10019070
	Hallucination, gustatory	10019071
	Hallucination, olfactory	10019072
	Hallucination, synaesthetic	10062824
	Hallucination, tactile	10019074
	Hallucination, visual	10019075
	Hallucinations, mixed	10019079
	Inappropriate affect	10021588
	Mood altered	10027940
	Mood swings	10027951
	Thinking abnormal	10043431
Non-specific	Acute psychosis	10001022
	Aggression	10001488
	Cognitive disorder	10057668
	Confusional state	10010305
	Delirium	10012218
	Delusional disorder, unspecified type	10012255
	Depersonalisation/derealisation disorder	10077805
	Disorientation	10013395
	Dissociation	10013457
	Disturbance in attention	10013496
	Disturbance in social behaviour	10061108
	Dopamine dysregulation syndrome	10067468
	Emotional disorder	10014551
	Flight of ideas	10016777
	Medication overuse headache	10072720

Category	Preferred Term	PT Code
	Mental impairment	10027374
	Narcotic bowel syndrome	10072286
	Paranoia	10033864
	Psychotic behaviour	10037249
	Psychotic disorder	10061920
	Sedation	10039897
	Stupor	10042264

APPENDIX 4. AE TERMS – DEPENDENCE (CUSTOM MedDRA QUERY)

Preferred Term	PT Code
Dependence	10012335
Drug dependence	10013663
Drug dependence, antepartum	10013675
Drug dependence, postpartum	10013676
Drug tolerance	10052804
Drug tolerance decreased	10052805
Drug tolerance increased	10052806
Substance dependence	10076595

APPENDIX 5. AE TERMS – WITHDRAWAL (CUSTOM MedDRA QUERY)

Preferred Term	PT Code
Abdominal pain	10000081
Agitation	10001497
Anhedonia	10002511
Anxiety	10002855
Arthralgia	10003239
Chills	10008531
Depressed mood	10012374
Depression	10012378
Diarrhoea	10012735
Drug detoxification	10052237
Drug rehabilitation	10064773
Drug withdrawal convulsions	10013752
Drug withdrawal headache	10013753
Drug withdrawal maintenance therapy	10052970
Drug withdrawal syndrome	10013754
Drug withdrawal syndrome neonatal	10013756
Dysphoria	10013954
Dyssomnia	10061827
Feeling of despair	10016344
Headache	10019211
Hyperhidrosis	10020642
Insomnia	10022437
Irritability	10022998
Morose	10027977
Mydriasis	10028521
Nausea	10028813
Negative thoughts	10058672
Nervousness	10029216
Obsessive thoughts	10029897
Pain	10033371

Preferred Term	PT Code
Persistent depressive disorder	10077804
Piloerection	10035039
Poor quality sleep	10062519
Rebound effect	10038001
Restlessness	10038743
Reversal of opiate activity	10039004
Rhinorrhoea	10039101
Steroid withdrawal syndrome	10042028
Syncope	10042772
Tachycardia	10043071
Terminal insomnia	10068932
Tremor	10044565
Vomiting	10047700
Withdrawal arrhythmia	10047997
Withdrawal syndrome	10048010
Yawning	10048232

APPENDIX 6. COVID-19 ANALYSIS

Pandemic has resulted in certain disruptions in the study conduct since early 2020, including site closure, delayed study drug supply, subjects discontinuation and missing assessments. These impacts were limited in scope upon review of the protocol deviations, and also confounded by the initiation of new regions. Sites in Ukraine and Russia were first initiated in March 2020 and July 2020. Therefore, only descriptive statistics will be provided to explore the potential impact of the pandemic on the primary and secondary objectives of the study. The following subgroup analysis (before vs during pandemic) will be conducted:

- Disposition
- Demographics and Baseline Characteristics
- Protocol Deviation
- Primary Efficacy Endpoint
- Key Secondary Endpoints
- TEAE
- SAE

Subjects enrolled before 01 Mar 2020 will be grouped as before pandemic, and subjects enrolled after this date will be grouped as during pandemic. While the pandemic has started in various regions a few weeks apart, a single cutoff date will be applied.

Signature Page for CLIN_ALK3831-A308-sap

Approved	Name: PPD Capacity: Other Date: 04-Dec-2023 19:59:22 GMT+0000
Approved	Name: PPD Capacity: Clinical Date: 04-Dec-2023 23:33:04 GMT+0000
Approved	Name: PPD Capacity: Clinical Date: 07-Dec-2023 12:34:29 GMT+0000
Approved	Name: PPD Capacity: Other Date: 07-Dec-2023 13:00:52 GMT+0000

Alkermes® Confidential Information

Document REG-026019

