11.1. Efficacy Endpoints

- Change from baseline in CGI-S by visit
- Time to discontinuation
- Change from baseline in IWQOL-Lite score by visit

| 12. | ASSESSMENT | OF PHARMA | COKINETICS |
|-------|------------|-----------------------|------------|
| L Z . | | () r filanyla | |

Not applicable.

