3.7. Efficacy Analyses

3.7.1. Efficacy Analysis

The following efficacy endpoints will be analyzed:

- Change from baseline in CGI-S score by visit
- Shift analysis in CGI-S
- Change from baseline in IWQOL-Lite scales (total score, physical function, self-esteem, sexual life, public distress, and work) by visit
- Time to treatment discontinuation

Value and change from baseline in CGI-S and IWQOL-Lite scores by visit will be summarized using descriptive statistics.

The IWQOL-Lite scale is a 31-item self-report measure of obesity-specific quality of life. IWQOL-Lite provides an overall total score as well as scores on five domains: (1) physical function, (2) self-esteem, (3) sexual life, (4) public distress, and (5) work. The raw scores will be transformed as follows (Tessier et al, 2012): the transformed scores range from 0 to 100, with 100 representing the best, and 0 representing the most impaired quality of life.

$$\text{Transformed Score} = \frac{\text{maximum theoretical score} - \text{actual score}}{\text{test score range}} \times 100$$

CGI-S response will be categorized into the categories summarized in [Table 1](#). The number and percentage of subjects in each category and with shifts from baseline will be summarized based on the observed data by descriptive statistics at 1, 3, 6, and 12 months. The shift categories are summarized in [Table 2](#).

Table 1: Definition of Shift CGI-S Categories

Response Category	CGI-S Score
Markedly to Extremely Ill	≥ 5
Moderately Ill	4
Normal to Mildly Ill	≤ 3

Table 2: Shift Categories for CGI-S response

Shift from Baseline Category for CGI-S Response	
Baseline Category	Shift Category
Markedly to Extremely Ill	
No change	
≥ 1 level improvement	
2 level improvement	
Moderately Ill	
No change	
1 level improvement	
1 level worsening	
Normal to Mildly Ill	
No change	
≥ 1 level worsening	
2 level worsening	

Time to treatment discontinuation will be analyzed using the Kaplan-Meier method and the KM plot will be provided. Both all-cause discontinuation and discontinuation due to AE will be summarized. For prematurely discontinued subjects (all cause or due to AE), time to event is defined as time from the date of first dose of study drug in study ALK3831-A308 to the date of last dose of study drug. Other subjects will be censored at the last dose of the study drug.

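### SAP Appendix 6 orders a before/during-pandemic display that mixes period with region, and names primary and key secondary endpoints that neither document defines

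*SAP*

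**What the plan says.** Appendix 6 of the SAP covers disruption from early 2020 onward. Its own assessment, after a review of protocol deviations, is that the impacts were small in extent and "also confounded by the initiation of new regions. Sites in Ukraine and Russia were first initiated in March 2020 and July 2020". From this it concludes that "only descriptive statistics will be provided to explore the potential impact of the pandemic on the primary and secondary objectives of the study".

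It then states: "The following subgroup analysis (before vs during pandemic) will be conducted". Seven items follow: disposition, demographics and baseline characteristics, protocol deviations, "Primary Efficacy Endpoint", key secondary endpoints, TEAEs and SAEs. Subjects enrolled before 01 Mar 2020 form one group and those enrolled after that date form the other, with one cutoff for all regions. No split, restriction or adjustment by region is attached.

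Elsewhere the endpoints are unranked. SAP 3.7.1 opens its list with "The following efficacy endpoints will be analyzed" and gives four: change in CGI-S, CGI-S shift, change in IWQOL-Lite and time to treatment discontinuation. Protocol 11.1 gives three: change in CGI-S, "Time to discontinuation" and change in IWQOL-Lite. Protocol 13.1 lists AE incidence, percent and absolute weight change, and waist circumference. SAP 3.7.4 calls its additional endpoints other, not secondary. Protocol Section 6 and SAP 1.1 each contain a primary objective only.

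**The concern.** There are two separate problems.

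The first is the comparison. The SAP identifies new regions as a confounder and then orders a contrast that contains it in full. Limiting the output to descriptive statistics removes the formal test but leaves the imbalance between the columns. A reader who sees different discontinuation or TEAE rates in the two columns cannot tell whether period or country produced them. Similar rates are no more informative, because a regional difference could offset a pandemic effect.

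The second is the instruction. Two of the seven items refer to endpoint categories that the trial does not have, and the stated purpose refers to objectives that it does not have. From the SAP text alone, a programmer cannot tell which tables to produce.

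**Working it through.** **Group membership.** Inputs, all from SAP Appendix 6: cutoff 01 Mar 2020; Ukraine and Russia sites first initiated in March and July 2020; grouping by enrolment date. A site not yet initiated cannot enrol, so these countries supply 0% of the before group. All their subjects fall in the during group, except anyone enrolled exactly on 01 Mar 2020. The rule places that date in neither group, since one group is before it and the other after it.

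**Whether another display separates region from period.** Where the SAP defines region levels (3.7.3 and 3.8.3.2), the split is US versus non-US. That does not isolate Ukraine and Russia, and it is not crossed with the pandemic grouping.

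**Size of the regional contribution.** Let s be the share of the during group from Ukraine and Russia, and d the difference in the outcome between those countries and the rest. Assume no pandemic effect, and that the remaining countries have the same mean m in both periods.

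- Before group: m
- During group: (1 − s) × m + s × (m + d) = m + s × d
- Difference shown: s × d

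The documents give neither s nor d. With assumed values, in percentage points:

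| s | d = 5 | d = 10 | d = 20 |
|---|---|---|---|
| 20% | 1.0 | 2.0 | 4.0 |
| 50% | 2.5 | 5.0 | 10.0 |
| 80% | 4.0 | 8.0 | 16.0 |

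The 16-fold range shows that the documents cannot fix the size. The plan states no figure of its own to reproduce.

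**Endpoint labels.** These are the places where a hierarchy could sit:

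- Protocol 6.1 and SAP 1.1.1: a primary objective, no secondary objective.
- Protocol 11.1 and 13.1: efficacy and safety lists, unranked.
- SAP 3.7.1: four efficacy endpoints, unranked.
- SAP 3.7.2 (multiplicity): not applicable.
- SAP 3.7.4: other endpoints.
- SAP Section 5 (changes from protocol): adds the CGI-S shift analysis and sets no order.

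None designates a primary efficacy or key secondary endpoint.

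**What the enrolment cutoff measures.** Protocol 8.1 and Table 3 give 24 to 48 months of treatment. SAP Tables 10 and 11 use 28-day months, so the planned length is 24 × 28 = 672 to 48 × 28 = 1,344 days. Taking enrolment as the start of dosing:

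- 672 days before 01 Mar 2020 is 29 Apr 2018. Anyone enrolled after that date and before the cutoff who completes 24 months is treated past the cutoff, yet is grouped as before.
- 1,344 days before the cutoff is 26 Jun 2016, earlier than the first consent that the protocol synopsis estimates (Q2 2017). On that timeline, every 48-month completer in the before group was treated past the cutoff.
- A subject enrolled on 01 Jul 2019 has 244 days before the cutoff. The share of planned treatment after it is (672 − 244)/672 = 64% for 24 months and (1,344 − 244)/1,344 = 82% for 48 months.

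The split therefore describes enrolment cohorts; it does not separate exposed from unexposed treatment time.

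**The case against.** The strongest reply is that Appendix 6 discloses the confounder and limits itself accordingly. The output is descriptive and exploratory, the study is single-arm and open-label, and SAP 3.1 presents results for all subjects as one group. This stands in part. The display cannot alter the main results, and a reader who inferred that regional confounding undermines the study's conclusions would go beyond the documents. Disclosure does not make the table interpretable, however, and a column split would help at little cost.

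A reader might also infer that the undefined endpoints would be picked once the data were known. The SAP approvals are dated December 2023 and completion was targeted for the fourth quarter of 2022, but the documents give no database lock date. SAP Sections 8 and 9 place programming specifications and mock tables in separate documents, which may name the endpoints. All the listed efficacy endpoints are reported for the full population anyway, so there is little room for selective reporting. Only the narrower statement is supported: the SAP text does not define the labels.

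Nor do the documents show that body weight is excluded. An undefined category cannot be known to leave it out, no document ranks weight above the other safety endpoints, and SAP 3.8.3.2 analyses it in full.

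Finally, restricting countries does not settle everything. It leaves the enrolment-date grouping in place, and the mix of antecedent studies may also shift with time: Protocol 5.1 describes A304 and A306 as ongoing while A307 had yet to begin. Both limits stand, and the first is why the fix goes beyond a country split.

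**Conclusion.** The point holds as a limitation of a supplementary display and as a drafting gap. Under the grouping rule, Ukraine and Russia appear only in the during column, so any difference combines region and period. This follows from the dates alone and needs no assumption. The size is s × d with neither input given; the 2 to 8 points from a 10-point difference and a 20–80% share illustrate the identity and do not estimate this trial's bias.

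The two endpoint entries and the mention of secondary objectives have no referent in either document, so that part cannot be carried out from the SAP as written. The grouping also counts as before the pandemic some subjects whose planned treatment lay mostly after the cutoff: 64–82% for a July 2019 enrolee who completes 24 to 48 months. The gap at 01 Mar 2020 is one calendar day and minor.

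**What to change.** Amend Appendix 6 as follows:

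- Show the before and during columns for countries that enrolled in both periods, and put Ukraine and Russia in a separate column. The main columns will have smaller n. The documents do not say which countries qualify, so check enrolment counts first.
- Replace the two undefined entries with endpoints already in the plan: change from baseline in CGI-S, time to discontinuation, change in IWQOL-Lite and percent change in body weight. Delete the reference to secondary objectives.
- Assign 01 Mar 2020 to one group.
- Label the groups as enrolment cohorts, or add a summary of events and discontinuations by calendar time on treatment before and after the cutoff, so that subjects enrolled earlier but treated mostly during the pandemic are not read as unexposed.

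The cost is SAP wording, a column split and, if chosen, one further summary from dates already collected. No new data are needed. The display remains descriptive, and differences in antecedent-study mix should still be noted when it is read.
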